8.1.3 Time-to-event analysis

Time-to-event analyses will be conducted for each Adverse Event of Interest.

Please refer to Section 3.6 for the assignment of treatment groups and to Section 3.2.1 for details on exposure times.

Cimzia vs. Comparator (acute event rules)

Per patient and Adverse Event of Interest, exposure time until the first occurrence of the AE is considered. Prior to the AE, at any given time after treatment start, the patient can be exposed to either of: Cimzia, Comparator, Overlap, or Gap (one at a time but with switches between them). Thus, up to the first occurrence of the AE, 4 exposure times are recorded, one for each treatment. The first occurrence of the AE is counted as event for the actual treatment where it occurred (i.e. exactly one of Cimzia, Comparator, Overlap, or Gap), and exposure time is censored for the remaining 3 treatments. If no AE of interest occurred, time will be censored at the end of exposure for all treatments. The comparison of interest is Cimzia vs. Comparator.

Any Cimzia vs. Comparator (acute event rules)

Per patient and Adverse Event of Interest, exposure time until the first occurrence of the AE is considered. Prior to the AE, at any given time after treatment start, the patient can be exposed to either of: Any Cimzia (i.e. Cimzia monotherapy or Overlap), Comparator, or Gap (one at a time but with switches between them). Thus, up to the first occurrence of the AE, 3 exposure times are recorded, one for each treatment. The first occurrence of the AE is counted as event for the actual treatment where it occurred (i.e. exactly one of any Cimzia, Comparator, or Gap), and exposure time is censored for the remaining 2 treatments. If no AE of interest occurred, time will be censored at the end of exposure for all treatments. The comparison of interest is Any Cimzia vs. Comparator.

Cimzia vs. Comparator (malignancy rules)

Per patient and Adverse Event of Interest, exposure time up to the first occurrence of the AE is considered. The attribution of the AE to Cimzia or Comparator follows the exposure rules as described in Section 3.2.1.1, i.e., if the patient was exposed to Cimzia, prior to the AE, the event will be systematically attributed to Cimzia, irrespective of actual treatment. If the patient was not exposed to Cimzia prior to the AE, it will be attributed to Comparator. Exposure to Comparator prior to a first treatment switch to Cimzia will be attributed to Comparator. As detailed in Section 3.2.1.1, Exposure time is measured from first exposure to Cimzia (or Comparator), irrespective of treatment gaps. If no AE of interest occurred, time will be censored at the end of exposure.

All time-to-event analyses are exploratory and not confirmatory. No formal hypothesis testing will be conducted. P-values are for descriptive purposes only.

The number and percentage of patients with AEs of interest, as well as those censored, will be displayed. Time-to-AEs of interest will be summarized using the Kaplan-Meier method and displayed graphically when appropriate. Median and 25th and 75th percentile event times, with corresponding 2-sided 95% confidence intervals as well as the range of event times will be provided by treatment group. The estimated hazard ratio, 2-sided 95% confidence interval and exploratory p-value will be provided.

8.1.4 Incidence and event rate calculation

In general, for each, the cumulative incidence, incidence rate and corresponding 95% confidence interval will be presented. For the incidence rate, the numerator will be the total number of patients experiencing the AE of interest for the first time in the study (if a patient switches treatment and has an AE of interest it will be considered a recurrence if the AE occurred while on a previous treatment). The denominator will be in 100 patient-years. That is, the denominator will be the total summation of individual patient-years at risk up the first occurrence of the AE of interest for subjects with that AE, and the total patient-years at risk for those subjects not experiencing that AE, divided by 100. Two-sided 95% confidence intervals for the incidence rates are calculated [using the GAMINV function in SAS] to determine the upper and lower limits for the number of events for each AE of interest, which is assumed to follow a Poisson distribution, divided by the total patient-years of exposure multiplied by 100. [Note that the method to be used follows a SAS implementation using the GAMINV function and is described in detail on bottom, right hand side of p. 2 and the code in the box on the left hand side of p. 3 in the SUGI paper <http://www2.sas.com/proceedings/sugi26/p241-26.pdf>].

A Poisson AE of interest regression analysis, accounting for within-patient correlations, implemented with the GENMOD procedure in SAS, is used to test for the differences in incidence rates between actual treatment cohorts at the two-sided $\alpha=0.05$ level. Potential code for these models is:

```
PROC GENMOD data = XXXXX;  
CLASS COHORT;  
MODEL AEOFINT = COHORT / D = POISSON OFFSET = LPRSNYRS;  
RUN;
```

Where AEOFINT is the number of events for a particular AE of interest, LPRSNYRS is the log of the total number of patient-years, and COHORT represents the actual treatment cohorts. Type III analysis will be used to get the cohort effects conditional on all covariates listed above in Section 4.1.

For event rates, the numerator will be the number of AEs of interest, including repeat occurrences in individual subjects. The denominator will be the total exposure in 100 patient-years, without censoring the exposure to the first event. That is, the total summation of individual patient-years divided by 100. No confidence intervals will be computed for event rates.

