4 REGISTRY STUDY PLAN

4.1 Investigator Selection Criteria

Selected gastroenterologists and internal medicine Investigators from both community-based and academic practice settings (75% and 25% respectively) will be approached to participate in this registry. Investigators will be asked to provide a confidentiality agreement, recruitment questionnaire, signed protocol signature page, signed study contract, Form FDA 1572, Financial Disclosure Form, current CV, and receive Institutional Review Board (IRB) approval prior to study activation. Once activated, Investigators will be able to consent patients using their IRB approved template and enroll patients into the study. Each Investigator should be able to recruit a minimum of 5 patients prescribed Cimzia and/or 5 patients prescribed other treatments.

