4.2 Selection of Study Population

This is a long-term observational study in the USA that includes a total of 3045 CD patients (1371 in the Cimzia Cohort and 1674 in the Comparison Cohort) as of Mar 2017. To ensure a sufficient number of Cimzia-treated patients in the registry, approximately half of enrolled patients will be receiving Cimzia for ≤ 12 months or about to receive Cimzia at the time of enrollment. The study will be conducted in all regions in the USA at approximately 280 enrolling investigative sites.

Recruitment of Cimzia-treated and comparator patients will be monitored and controlled as needed in order to ensure balanced enrollment over time.

Quarterly progress reports will be sent to the FDA during the patient recruitment period.

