4.5 Schedule of Assessments

No mandatory visits are required as part of this protocol. All visits will be scheduled and conducted per sites standard of care. Standard of care is defined as: A diagnostic and

customary clinical treatment/practice process that a clinician should follow for a Crohn's disease patient, a certain type of illness, or clinical circumstance.

Investigators will complete the baseline data for each patient after enrollment into the study and includes the signing of the Informed Consent Form (ICF). Follow-up data for patient visits will be reported in accordance to sites standard of care or clinical judgment appointments. Telephone contacts are permitted. All data, as described in Section 4.8.2, are to be collected as available during the telephone contacts.

In an effort to minimize missing data and unreported events over the 8-year Follow-Up Period, patients will directly report data in parallel to the Investigator reported data. Direct patient follow-up will occur every 3 months after enrollment (months 3, 6, 9, 12, etc) via a web-based system, by mail or by phone - as preferred by the patient. If a patient does not provide the information via the web, mail or by phone within approximately 1 week after the 3 month due date, the study patient interview service will call the patient to obtain the required information over the phone. Safety information collected directly from the patient will be available for the study investigative site to review. If 8 consecutive quarterly patient surveys have not been at least partially completed, further attempts at patient contact are not required. The Investigator will be requested to confirm whether the patient status should be changed to 'Lost to Follow-up'.

	Study Entry (Baseline)	Investigator- Reported Follow- up ^b	Direct Patient Follow-up Year 1-8
	ENROLLMENT	PER STANDARD OF CARE	EVERY 3 MONTHS
Written informed consent	X		
Assessment of inclusion/exclusion criteria	X		
Demography	X		
Crohn's disease history	X		
Medical and surgical history	X		
Family history	X		
Reason for initiating Cimzia or other medication	X		
Planned Cimzia or other medication treatment period	X	X	
CD treatment medication changes and reason		X	X
Concomitant medications	X	X	X
All SAEs and AEs of interest since time of last completed follow-up ^a		X	

	Study Entry (Baseline)	Investigator- Reported Follow- up ^b	Direct Patient Follow-up Year 1-8
	ENROLLMENT	PER STANDARD OF CARE	EVERY 3 MONTHS

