4.7 Participation and Retention Strategies

Individual patient follow-up is approximately 8 years after enrollment, regardless of discontinuation of Cimzia or other medications.

As a means to retain patient participation, patients are followed up directly via a web-based system or if preferred, by mail (including a prepaid self-addressed return envelope) or by the phone every 3 months throughout the study (unless the patient withdraws consent or is deemed lost to follow-up) to complete a patient survey. “Lost to follow-up” is defined as a patient who goes 2 years with no data being collected/reported (2 years without Investigator visit/telephone contact or failure to at least partially complete 8 consecutive quarterly patient surveys; further attempts at patient contact are not required). The patients will receive emails or postal mail reminding them to complete the survey. If they have not completed the survey one week after the due date, they will be called by the independent patient interview service to complete the survey via phone. Patients completing the quarterly surveys will receive a nominal appreciation gift (if approved by the site’s IRB).

In the event an Investigator retires, or discontinues participation from the registry, the following transition plan is in place to enable continuing participation of their patients. The Informed Consent Form include wording explaining that if the patient’s Investigator discontinues participation in the registry, or retires, the independent patient interview service will be notified and the name and contact information of the closest participating study Investigator that they can contact during the remainder of their participation in the registry. The new Investigator and the patient should document re-consent of the transition. The registry can continue to collect the direct patient-reported data without the need for re-consent. If the patient is unable or unwilling to be followed by a new Investigator, the patient must be discontinued from the study.

In the event a patient moves to a new location or chooses to leave their current Investigator, patients are provided with information upon enrollment as to how to locate a participating Investigator in their area or how to provide the registry information to a new Investigator that may not yet be participating. Participating patients will have access to all of this information on the study specific web portal.

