4 STATISTICAL/ANALYTICAL ISSUES

4.1 Adjustments for covariates

Conventional multiple regression analysis and propensity score analysis will include (but are not limited to) the following Baseline characteristics in the initial run of the model.

Characteristics that are continuous will remain as such. Categorical variables will use the values in parentheses:

- Age
- Gender (Male, Female)
- Race (American Indian/Alaskan native, Asian, Black, Native Hawaiian/Pacific Islander, White, Other/Mixed)
- Smoking status (Never, Current, Former)
- Other biologic treatment use in the year prior to Baseline (Yes, No)
- Immunosuppressant use in the year prior to Baseline (Yes, No)
- Corticosteroid use in the year prior to Baseline (Yes, No)
- Disease extent (Ileum, Colon, Illeocolon, Upper GI, Ileum + upper GI, Colon + upper GI, Illeocolon + upper GI, Other)
- Diagnosed with fistulas (Yes, No)
- Duration of disease
- Physician assessment of disease severity (Remission, Mild-moderate, Moderate-severe, Severe)
- Number of Crohn's related hospitalizations in the year prior to Baseline
- Number of surgical resections in the year prior to Baseline
- Calendar year of enrollment

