4.5 Examination of subgroups

The primary analysis for acute events will be stratified on incidence/prevalence use (yes/no).

The impact of data from the high accruing study site #849 on key outcomes will be assessed (Clinical site closed due to significant noncompliance; reported to FDA's Division of Scientific Investigations in letter dated 29 April 2020).

If sufficient power exists, further stratification based on duration of prevalent use (e.g., 1-5 months, 6+ months, etc.) may be performed. This is described in more detail in Section [8.1.5](#).

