5 STUDY POPULATION CHARACTERISTICS

5.1 Subject disposition

The number and percentage of patients who enrolled and the number and percentage of patients who completed the study will be presented, together with the number and percentage of patients who withdrew from the study prematurely and a breakdown of the corresponding reasons for discontinuation will be produced by enrollment cohort and actual treatment at Baseline.

A Cox proportional hazards model utilizing Kaplan-Meier methods for time to discontinuation by year 1, year 2, ..., year 8, will be performed by enrollment cohort and actual treatment at Baseline. Discontinuation status, discontinuation time (median, 25th and 75th quartiles and corresponding two-sided 95% confidence intervals), and a hazard ratio and exploratory p-value from a log-rank test at $\alpha=0.05$ overall significance level will be included for the analysis of each year.

A Cox proportional hazards model utilizing Kaplan-Meier methods for time to discontinuation by year 1, year 2, ..., year 8, will be performed by enrollment cohort and actual treatment at Baseline. Discontinuation status, discontinuation time (median, 25th and 75th quartiles and corresponding two-sided 95% confidence intervals), and a hazard ratio and exploratory p-value from a log-rank test at $\alpha=0.05$ overall significance level will be included for the analysis of each year.

A summary of expected and actual patient retention by enrollment cohort and actual treatment at Baseline will include total patient-years and the number of patients followed for at least 1 year, at least 2 years, ..., at least 8 years.

Time to discontinuation will be analyzed using two different censoring rules (A and B).

According to censoring rule A, the time for patients in the Cimzia cohort will be censored when they switch to Comparator treatment and the time for patients in the Comparator cohort will be censored when they switch to Cimzia treatment. According to censoring rules B, time for all patients will be censored when they switch from one biologic treatment to another biologic treatment.

A table summarizing the number and percentage of patients enrolled at each site by enrollment cohort will be presented.

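### The Poisson, Cox and log-rank comparisons name no handling of correlation within the roughly 280 sites, so intervals can be too narrow for commoner acute events and for discontinuation if treatment clusters by site

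*SAP*

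**What the plan says.** **Site structure.** Protocol 4.2: "The study will be conducted in all regions in the USA at approximately 280 enrolling investigative sites". SAP 2.4 gives 3076 patients at the final analysis.

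**Ways in which site enters.**
- Treatment: the Investigator chooses it (Protocol 4.4). Recruitment may be to one cohort or both: "Each Investigator should be able to recruit a minimum of 5 patients prescribed Cimzia and/or 5 patients prescribed other treatments".
- Events: no visit is mandatory, and "Follow-up data for patient visits will be reported in accordance to sites standard of care or clinical judgment appointments". SAP 8.2.2 counts events from the investigator or the drug safety database and leaves out events known only from the patient survey.
- Exit: Investigators may withdraw patients (Protocol 4.4). When an Investigator leaves, a transfer route exists, but "If the patient is unable or unwilling to be followed by a new Investigator, the patient must be discontinued from the study".

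**Comparative analyses.**
- SAP 8.1.4: "A Poisson AE of interest regression analysis, accounting for within-patient correlations, implemented with the GENMOD procedure in SAS". The potential code that follows has one CLASS variable (COHORT), no REPEATED statement and no site term.
- SAP 8.1.3: hazard ratios, intervals and p-values, with up to four exposure records per patient. No variance method is named.
- SAP 8.1.5: rate ratios with 95% CIs from regression. No cluster is named.
- SAP 5.1, on discontinuation: "a hazard ratio and exploratory p-value from a log-rank test at $\alpha=0.05$ overall significance level will be included for the analysis of each year".
- SAP 4.1 and 8.1.2: 14 named covariates, without site.

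**Where site is used.** SAP 5.1 tabulates enrolment by site and cohort. SAP 4.5 adds one check: "The impact of data from the high accruing study site #849 on key outcomes will be assessed".

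**The concern.** Patients at one site share an Investigator, a visit rhythm and a reporting habit. If sites differ in recorded event rates and also in how often they use Cimzia, the Cimzia-comparator contrast is partly a contrast between sites. Its true variance then exceeds the variance computed for independent patients. Both conditions are needed: if sites mix the two treatments evenly, site effects largely cancel from the contrast.

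The likeliest places for this to matter are the commoner acute events, such as serious infections, and discontinuation, where a site closure can remove several patients together. In a descriptive safety registry the interval carries most of the message, so an interval that is too short overstates what the registry has shown.

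**Working it through.** **Inputs from the documents.** About 280 sites; 3045 patients in March 2017 (1371 Cimzia, 1674 comparator) and 3076 at the end; 8% annual drop-out; 8 years of follow-up; two-sided 0.05.

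**Not in the documents, so assumed and varied.** Outcome ICC, treatment ICC (how far Cimzia use clusters by site), the site-size distribution, event rates, the switching fraction and site-closure rates. There is no planned design effect or clustered standard error to reproduce.

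**Step 1: rates implied by the stated power.** With 12,500 patient-years per arm and exactly 80% power, the control rate is (1.96 + 0.842)² × (1/12,500) × (1 + 1/RR) / (ln RR)².
- Solid malignancy, RR 1.56: 7.85 × 0.00008 × 1.641 / 0.198 = 0.0052, about 0.5 per 100 patient-years.
- Serious infections, RR 1.5: 7.85 × 0.00008 × 1.667 / 0.164 = 0.0064, about 0.6 per 100 patient-years.

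The plan says at least 80%, so these rates cannot be confirmed. The 4 per 100 patient-years used below for a commoner event is an assumption well above 0.6.

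**Step 2: simple design effect.** DE = 1 + (m − 1) × ICC(outcome) × ICC(treatment), with m = 3045/280 = 10.9. At outcome ICC 0.05:
- treatment ICC 0: DE = 1.00
- treatment ICC 0.1: DE = 1 + 9.875 × 0.05 × 0.1 = 1.05
- treatment ICC 0.3: DE = 1.15
- treatment ICC 1 (single-cohort sites): DE = 1.49, so intervals should be √1.49 = 1.22 times as wide

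Unequal site sizes raise these values.

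**Step 3: simulation with no treatment effect.** Settings: 3076 patients, 280 sites of skewed (gamma) size, 45% Cimzia, and a gamma site effect with variance 0.25, which is an outcome ICC of about 0.05 at 4 events per 100 patient-years. There were 1500 replicates per setting, so the simulation error near 5% is √(0.05 × 0.95/1500) = 0.6 points. The table gives rejection rates of the nominal 5% naive test.

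| Scenario | Treatment ICC 0.1 | 0.3 | 0.5 | 1 | Range over repeat runs | Range with one site at 8% of patients |
|---|---|---|---|---|---|---|
| 4 per 100 p-y, cohorts fixed | 4.7% | 7.1% | 11.1% | 15.8% | 5-16% | 6-23% |
| 4 per 100 p-y, half of patients switch once | 5.2% | 4.8% | 6.6% | 7.8% | 5-9% | 6-12% |
| 0.5 per 100 p-y, cohorts fixed | 5.6% | 5.5% | 5.0% | 6.8% | 4-8% | 4-8% |

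Cross-check: the simulated variance inflation in the first row runs from 1.1 to 1.9. An inflation of 1.9 implies 2 × Φ(−1.96/√1.9) = 2 × Φ(−1.42) = 15.5%, in line with 15.8%.

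**Step 4: sensitivity to the site spread and rate.** A second simulation used 3045 patients and a site-effect CV of 0.5 (variance 0.25) or 1.0, with equal or skewed site sizes.
- At 0.6 per 100 patient-years and CV 0.5: 5.5-5.9% with partly clustered treatment (treatment ICC 0.4) and 6.7-6.9% with single-cohort sites. At CV 1.0: 7.6-11.0% and 10.1-14.2%.
- At 0.5 per 100 patient-years, CV 1.0 and single-cohort sites: 9.3-13.3%.
- With treatment evenly mixed within sites and CV 0.5: 4.6-5.5% at 0.6 to 3 per 100 patient-years.

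**Step 5: discontinuation.** Assume 1, 2 or 3% of sites close per year, within the 8% total drop-out. If every patient of a closing site leaves, the naive test rejects 9.6, 11.8 and 16.3% at treatment ICC 0.1, and 17.1, 24.3 and 29.3% at 0.3. If half transfer, it rejects 6.5-12.1%.

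**Step 6: remedy.** Variance clustered on site gave about 4-7% in the scenarios of Steps 3 and 5.

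**The case against.** **The gap is an inference from silence.** The Cox variance method is not given, the code is only potential code, and the covariate list is open-ended. This stands in part. But a plain log-rank test takes no covariates, the Poisson text names its correlation level and stops at the patient, and SAP 8.1.2.1 says the listed variables were chosen in advance.

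**Intervals need not be too narrow.** A reader might infer that they certainly are. The documents do not support that: sites may enrol both cohorts, and no ICC or cohort mix by site is given. At low treatment clustering the naive test is close to nominal.

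**Malignancy, the primary outcome, is little affected.** This stands at the site spread assumed in Step 3. Only single-cohort sites with much wider site differences gave more (Step 4).

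**Acute-event person-time follows actual treatment.** Patients move between Cimzia, comparator, overlap and gap (SAP 3.6, 8.1.3), which adds contrast within patient and within site. This stands and roughly halves the upper end.

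**Ascertainment is partly standardised.** There are quarterly surveys run by an independent service, CRO contact with sites and biopsy confirmation of malignancy (Protocol 4.7, 4.8.2, 5.2.4). These help, but a survey event still needs the Investigator's confirmation to count (Protocol 5.4, SAP 8.2.2).

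**Drop-out does not have to come in whole-site blocks.** This stands: Protocol 4.7 provides for transfer, so the figures with all patients leaving are a worst case.

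**The tests are descriptive.** This stands (SAP 3.1, 8.1). The consequence is overstated precision, not a wrong confirmatory decision. The check on site #849 partly covers a dominant site but does not change standard errors.

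**Conclusion.** The gap is real and the remedy is cheap; it is an improvement and does not invalidate the plan. No planned comparison states how site correlation is handled, while the documents tie treatment choice, event recording and exit to the site or its Investigator.

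The effect is conditional on treatment clustering by site. For a commoner acute event it can be material, up to the Step 3 upper ends, but those rest on an assumed 4 per 100 patient-years and ICC of 0.05. If serious infections occur nearer the 0.6 implied by the power statement, inflation is smaller. For malignancy it is small, and with even mixing within sites it is near nil. For discontinuation it depends on closure and transfer rates that the plan does not give.

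A reader might also infer that differences in site reporting could pass for a Cimzia effect and that a clustered variance would cure this. The documents make such confounding possible but do not show it, and robust variance leaves the point estimate unchanged. That needs the separate site-stratified analysis.

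**What to change.** In SAP 5.1, 8.1.3, 8.1.4 and 8.1.5, state that all Cimzia-comparator rate ratios, hazard ratios, confidence intervals and p-values use robust (sandwich) variance clustered on enrolling site.

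- Poisson: add site to CLASS and use `REPEATED SUBJECT=site` in GENMOD.
- Cox: use `COVS(AGGREGATE)` with `ID site` in PHREG.
- Because patients are nested in enrolling sites, this also covers repeated records within patient and so supplies what the sample code in 8.1.4 lacks.
- In 5.1, replace the log-rank p-value with the site-clustered Cox p-value.
- For endpoints with events at few sites, where the sandwich is unstable, show the model-based interval with a note. Fix the cut-off in advance; none has been tested here.
- Add a site-stratified sensitivity analysis for serious infections and discontinuation.

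Cost: SAP wording and one or two SAS statements per model, using a site identifier already recorded. Intervals become somewhat wider, and single-cohort sites contribute little or nothing to the stratified analysis.

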8.1 Statistical analysis of the primary endpoints

The primary analysis of this study is descriptive and no formal hypothesis testing will be conducted. For the primary analysis, adverse event rates will be calculated by dividing the number of reported safety events by the patient-years at risk. Cimzia-specific rates will be calculated and compared to all other CD treatment rates.

Propensity scores will be used to assess the comparability of patients who are receiving Cimzia at baseline to those who are receiving another CD medication. Appropriate analytical methodologies will be used to investigate the effect of time varying confounders.

Time-to-event analyses for each Adverse Event of Interest will be conducted using Cox proportional hazard modeling and Kaplan-Meier curves.

Analyses of specific outcomes may be conducted if appropriate.

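### The Cox hazard ratios in SAP 8.1 and 8.1.3, including those for malignancy, are not tied to any of the plan's adjustments for confounding

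*SAP*

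**What the plan says.** SAP 8.1 states: "Time-to-event analyses for each Adverse Event of Interest will be conducted using Cox proportional hazard modeling and Kaplan-Meier curves". Section 8.1.3 defines three exposure-based contrasts (two under the acute-event rules, one under the malignancy rules) and then says: "The estimated hazard ratio, 2-sided 95% confidence interval and exploratory p-value will be provided". It adds: "All time-to-event analyses are exploratory and not confirmatory". Neither section names a covariate, a propensity score or a matched population for these models.

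SAP 8.1.4 plans a Poisson regression, "accounting for within-patient correlations, implemented with the GENMOD procedure in SAS", which "is used to test for the differences in incidence rates between actual treatment cohorts". It continues: "Type III analysis will be used to get the cohort effects conditional on all covariates listed above in Section 4.1". The sample code in the same section, offered only as potential code, has the model line "MODEL AEOFINT = COHORT / D = POISSON OFFSET = LPRSNYRS" and the key: "Where AEOFINT is the number of events for a particular AE of interest, LPRSNYRS is the log of the total number of patient-years".

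Protocol 6.4.1 says that propensity scores will form part of the primary analysis. Protocol 6.4.1.2 makes Cox modelling the primary analysis for acute events. SAP 8.1 keeps the use of propensity scores to judge comparability but not their place in the primary analysis.

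**The concern.** Treatment is not randomised, and protocol 6.4.1.3 itself warns that patients may differ substantially between treatments in ways that affect outcomes. A hazard ratio with a confidence interval and p-value for malignancy, the primary outcome, will be read as a comparison of treatments. If nothing says that it is adjusted, a programmer following 8.1.3 will fit treatment alone. The report would then show a crude hazard ratio and an adjusted rate ratio for the same event. Where the two differ, the plan would not say which to rely on, and the reader could not tell confounding from a difference in method.

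**Working it through.** **1. Where each planned adjustment is attached**

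- SAP 4.1 (covariate list): conventional multiple regression and propensity score analysis. Cox is not named.
- SAP 8.1.2.3: covariates still out of balance enter an outcome regression whose only stated outcome is serious infections.
- SAP 8.1.2.4: covariates still out of balance after matching enter a final analysis of cohort effects. Neither model nor outcome is given.
- SAP 8.1.4 text: the Poisson model, conditional on the 4.1 covariates.
- SAP 8.1.5: rate ratios from multivariable regression.
- SAP 3.5.3: defines a Propensity Score Set, but no analysis section names it. Sections 3.5.1 and 3.5.2 assign all analyses to the Enrolled Set and the Full Analysis Set respectively.
- SAP 4.5 and 8.1.5: the acute-event primary analysis is stratified by incident or prevalent use. This covers acute events only and does not replace the 4.1 covariates.

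None of these refers to the hazard ratios in 8.1.3.

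**2. Can the link be inferred?** For acute events, partly: protocol 6.4.1 and 6.4.1.2 read together put propensity scores into a Cox primary analysis. SAP 8.1 instead describes the primary analysis as event rates. For malignancy, protocol 6.4.1.1 does not mention Cox, so no such route exists.

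**3. Illustration of size.** The plan states no figure to reproduce, and the documents do not give the imbalance between cohorts. The only document input is the 0.2 limit on absolute standardized bias (SAP 8.1.2.4). All other inputs are assumed, and the true ratio is set to 1.

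*Age.* Assume an SD of 10 to 15 years, equal in both groups, and a hazard multiplied by h = 1.5 to 2.5 per decade. Gap = 0.2 × SD = 2 to 3 years. Apparent ratio = h^(gap/10).

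- 2-year gap: 1.5^0.2 = 1.08; 2^0.2 = 1.15; 2.5^0.2 = 1.20
- 3-year gap: 1.5^0.3 = 1.13; 2^0.3 = 1.23; 2.5^0.3 = 1.32
- Opposite direction: 1/1.316 = 0.76 to 1/1.084 = 0.92
- At half the limit (0.1): 1.5^0.1 = 1.04 to 2.5^0.15 = 1.15

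*Binary risk factor.* Assume prevalence p0 of 10 to 40% in one group and a risk ratio RR of 1.5 to 2.5. Solve (p1 − p0)/√(0.5[p1(1−p1) + p0(1−p0)]) = 0.2 for p1. This gives 10% v 16.8%, 20% v 28.5%, 30% v 39.5% and 40% v 49.9%. Apparent ratio = [1 + p1(RR−1)]/[1 + p0(RR−1)].

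- Smallest (10%, RR 1.5): 1.084/1.050 = 1.03
- Largest (20%, RR 2.5): 1.4275/1.300 = 1.10; the 30% case also gives 1.10
- Opposite direction: 1/1.098 = 0.91 to 1/1.032 = 0.97

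**4. Size of the covariate set.** Counting SAP 4.1 with calendar year as continuous: race 5, smoking 2, disease extent 7, severity 3, and ten single-parameter terms. Total 5 + 2 + 7 + 3 + 10 = 27, before the treatment term. SAP Table 8.1 lists 16 event types, several likely to be rare, so full adjustment will not be workable for all of them.

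**5. The 8.1.4 code against its paragraph.** The text asks for 4.1 covariates, Type III tests and within-patient correlation. The code has COHORT alone, no TYPE3 option, and no REPEATED statement or patient identifier. The test is of incidence rates, which the section defines by first events and time up to the event; the key speaks of number of events and total patient-years. In context first events are meant, and then the missing clustering hardly matters. In a null simulation (2,000 runs per setting, 1371 and 1674 patients; assumed 5 events per 100 patient-years, follow-up 0.5 to 8 years, gamma frailty variance 0 to 4, none or 30% switching), the model without clustering rejected in 4.5 to 5.9% of runs and the clustered version in 4.3 to 5.8%.

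**The case against.** The case on the other side is substantial.

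- Adjusted estimates are already planned (8.1.4 text, 8.1.5), and the SAP's Amendment 5 rationale aligns the time at risk of the two analyses. The crude hazard ratio would not stand alone.
- All time-to-event analyses are exploratory, and SAP 2.1.1 rules out formal hypothesis testing.
- SAP 1 says that the plan is to be read with the protocol, which supplies the propensity-score link for acute events. SAP 8.1 also promises suitable methods for time-varying confounders.
- The final analysis in 8.1.2.4 may be meant to include Cox.

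The first two points stand and limit the consequence. The third narrows the gap for acute events but not for malignancy, and the sentence on time-varying confounders names no method or model. The fourth is possible but unstated: the adjustments are not tied to the hazard ratios, which is different from being excluded.

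A reader might infer three stronger claims, and the documents support none of them. The first is that the SAP leaves confounding unaddressed; it plans propensity score analyses and adjusted rate ratios. The second is that the sample code shows the Poisson analysis will be unadjusted or will have an inflated error rate; the code is only illustrative, the prose requires both features and should govern, and for first events clustering is negligible. The third is that the hazard ratios are biased against Cimzia; the documents give neither the direction nor the size of the imbalance.

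**Conclusion.** The point holds and should be fixed. As written, SAP 8.1.3 yields crude hazard ratios for malignancy and the other AEs of interest in a non-randomised comparison, while the adjustments that the trial has planned are attached to other estimates. The gap is clearest for malignancy, where no protocol text links propensity scores to a Cox model.

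The bias cannot be computed from the documents. The illustrative ranges (1.08 to 1.32 or 0.76 to 0.92 for age; 1.03 to 1.10 or 0.91 to 0.97 for a binary factor) rest on assumed risk effects and on the SAP's tolerance for imbalance, not on observed imbalance, which may be smaller or larger.

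The incomplete code is a minor matter. So is the cross-reference to SAP 3.6, which defines the hazard ratio by treatment at baseline while 8.1.3 uses exposure. The Amendment 5 rationale indicates that the exposure-based contrasts govern AEs of interest.

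**What to change.** 1. In SAP 8.1.3, state that the hazard ratios for malignancy and acute events are adjusted for the Section 4.1 covariates, or for the propensity score when events per model parameter fall below a number set in advance. Show the crude hazard ratio alongside and the Propensity Score Set result as supporting. Note that the score and the matching rest on baseline cohort, so neither guarantees balance once exposure is reassigned at switches.
2. In SAP 8.1.2.3, replace the reference to serious infections with malignancy and each AE of interest.
3. Minor: in the 8.1.4 code, add the 4.1 covariates and TYPE3, define the outcome as a first event and the offset as log time at risk to that event, and add REPEATED by patient where a patient supplies several rows. State that the baseline contrast in 3.6 does not govern the 8.1.3 hazard ratios; it fits the time-to-discontinuation analysis in 5.1.

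Cost: a short SAP edit and a few lines of SAS, using covariates already collected. The downsides are wider intervals for rare events and the need for a rule on missing baseline covariates, which SAP 4.2 does not give.
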